6.3. Safety Analyses

The type, severity, duration and frequency of reported ocular adverse events will be tabulated for each group. Adverse events will also be summarized for events that were considered treatment-related. Comparison of treatment groups with respect to the proportion of study patients reporting adverse events will be made using Fisher's Exact Test.

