4. INCLUSION/EXCLUSION CRITERIA

4.1. Inclusion Criteria:

Subjects **MUST** fulfill the following conditions to qualify for enrollment into the trial

1. Subject is undergoing bilateral lens extraction with intraocular lens implantation of the Symphony with InteliLight in the dominant eye and a Synergy in the non-dominant eye.
2. Gender: Males and Females.
3. Age: 50 years and older.
4. Willing and able to provide written informed consent for participation in the study
5. Willing and able to comply with scheduled visits and other study procedures.
6. Scheduled to undergo standard cataract surgery with topical anesthesia in both eyes within 2 to 30 days between surgeries
7. Subjects who require an IOL power in the range of +5.00 D to +34.0 D only.
8. Subjects who require a toric IOL up to +3.75 D at the IOL plane (2.57 D corneal plane).
9. Potential postoperative visual acuity of 0.2 logMAR (20/32 Snellen) or better in both eyes.

4.2. Exclusion Criteria:

Subjects with **ANY** of the following conditions on the eligibility exam may **NOT** be enrolled into the trial.

1. Severe preoperative ocular pathology: amblyopia, rubella cataract, proliferative diabetic retinopathy, shallow anterior chamber, macular edema, retinal detachment, aniridia or iris atrophy, uveitis, history of iritis, iris neovascularization, medically uncontrolled glaucoma, microphthalmos or macrophthalmos, optic nerve atrophy, macular degeneration (with anticipated best postoperative visual acuity less than 20/30), advanced glaucomatous damage, etc.
2. Uncontrolled diabetes.
3. Use of any systemic or topical drug known to interfere with visual performance.
4. Contact lens use during the active treatment portion of the trial.
5. Any concurrent infectious/non-infectious conjunctivitis, keratitis or uveitis.
6. Clinically significant corneal dystrophy
7. History of chronic intraocular inflammation.
8. History of retinal detachment.
9. Pseudoexfoliation syndrome or any other condition that has the potential to weaken the zonules.
10. Previous intraocular surgery.
11. Previous corneal refractive surgery (i.e. LASIK, PRK, RK).
12. Previous keratoplasty
13. Severe dry eye
14. Pupil abnormalities
15. Anesthesia other than topical or peribulbar anesthesia (i.e. retrobulbar, general, etc).
16. Any clinically significant, serious or severe medical or psychiatric condition that may increase the risk associated with study participation or may interfere with the interpretation of study results.

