17. Participation in (or current participation) any ophthalmic investigational drug or ophthalmic device trial within the previous 30 days prior to the start date of this trial.

The principal investigator reserves the right to declare a patient ineligible or non-evaluable based on medical evidence that indicates the patient is unsuitable for the trial.

4.3. Exclusion Criteria at time of surgery:

If any of the following exclusion criteria are applicable to the study eye, the subject should not continue in the study.

1. Other ocular surgery procedures, i.e. iStent, anterior vitrectomy
2. Significant vitreous loss
3. Significant anterior chamber hyphema
4. Uncontrollable intraocular pressure
5. Zonular or capsular rupture

6. Bag-sulcus, sulcus-sulcus or unknown placement of the haptics
7. Suturing of incision required at time of surgery
8. Intraocular lens tilt or decentration
9. Significant sedation or retrobulbar block during surgery
10. Other procedure, such as pupil stretch, expanders, iris hooks during surgery

Note: Any subject in which surgery has been aborted for either eye should immediately be discontinued from the study and an exit form completed for that subject. These subjects will be followed up as per the clinic standard of care, monitored for safety, and their data will be excluded from the study efficacy analysis (obtained from FDA Database Research Results Feb, 05, 2009). All adverse events will be appropriately documented and reported.

Additionally, participants who are considered to be a vulnerable subject population are not to be enrolled into the study without prior written authorization from both the Sponsor and the IRB to ensure that a description of additional safeguards are in place during the consenting and enrollment processes. Vulnerable populations include, but are not limited to, the following:

1. Prisoners
2. Nursing home residents /institutionalized individuals
3. Mentally disabled /cognitively impaired individuals
4. Sponsor employees and their family members
5. Site employees and their family members that are directly and indirectly involved with the study
6. Students of the university or the principal investigator participating in the study
7. Economically and/or educationally disadvantaged individuals
8. Comatose individuals / traumatized individuals
9. Adults who do not read and/or write
10. Hearing impaired individuals
11. Terminally ill individuals / individuals with life-threatening conditions

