5.5. Study endpoint criteria

5.5.1. Patient Completion of Study: If a study patient has completed the final visit (Visit 3) of the study, he/she is considered to have completed the study.

5.5.2. Patient Discontinuation: Each study patient may voluntarily discontinue the study at any time they choose. Study patients who cannot complete the study for administrative reasons (e.g., non-compliance, failure to meet visit schedule, etc.) will be discontinued from the study. Study patients discontinued during the enrollment phase (prior to surgery) of the study will be replaced. Subjects who are discontinued after first eye surgery before second eye surgery will also be replaced.

5.5.3. Patient Termination: A study patient will be terminated if the study patient develops any severe adverse event that may be related to the study. A study patient will receive appropriate treatment at the discretion of the investigator. Notification of termination will be clearly documented. These study patients are considered to have completed the study and will not be replaced.

5.5.4. Study Termination: The investigator with appropriate notification may terminate the study. If, after clinical observations, the investigator feels that it may be unwise to continue the study, he may stop the study.

5.5.5. Study Completion: The study will be complete when all enrolled patients have completed Visit 3 or have been terminated from the study.

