6. STATISTICAL CONSIDERATIONS

6.1. Sample size

A total of 40 subjects will be enrolled. In order to calculate the sample size, we need to know an accurate estimate of the standard deviation of the outcome measure which we do not know; therefore, we consider this study a pilot trial. When estimating the sample size for a pilot study, the simplest method is to apply a sample size rule of thumb.

Browne suggests a general flat rule to 'use at least 30 subjects or greater to estimate a parameter'.

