6.2. Statistical Analysis

All data will be collected by the site and entered into a database. Subjects will be assigned an ID number. Data analysis will be performed without patient identification. Statistical analysis will be performed using standard descriptive statistics and other tests as deemed appropriate based on the characteristics of the data to be analyzed. All statistical tests will be two-sided and interpreted at a 5% significance level. Vision satisfaction, spectacle independence and visual symptoms will be compared to a historical control of patients implanted bilaterally with Synergy OU. Data analysis will be conducted by a third-party consultant.

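### Section 6.3 plans a Fisher's exact comparison of adverse event proportions between treatment groups, but the trial has one cohort and no second group for adverse events

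*Combined protocol and SAP*

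**What the plan says.** Section 6.3 contains two statements that presuppose groups. The first is descriptive: ocular "adverse events will be tabulated for each group". The second is a test with the patient as the unit: "Comparison of treatment groups with respect to the proportion of study patients reporting adverse events will be made using" Fisher's exact test. Section 6.3 does not say what the groups are, and it gives no denominator for the proportion.

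The design sections describe one group. Section 3 calls the study non-randomized and bilateral. Inclusion criterion 1 in Section 4.1 requires "implantation of the Symphony with InteliLight in the dominant eye and a Synergy in the non-dominant eye", and Section 5.3 repeats that allocation for all subjects. Section 6.1 gives a single unsplit number: "A total of 40 subjects will be enrolled". Section 9.3, on assigning subjects to groups, is marked not applicable.

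The only other patients mentioned are in Section 6.2: "Vision satisfaction, spectacle independence and visual symptoms will be compared to a historical control of patients implanted bilaterally with Synergy OU".

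Two further rules bear on the denominator. For subjects whose surgery is aborted, Section 4.3 says "their data will be excluded from the study efficacy analysis", and also "All adverse events will be appropriately documented and reported". Section 5.5.2 adds: "Subjects who are discontinued after first eye surgery before second eye surgery will also be replaced".

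**The concern.** A Fisher's exact test on proportions of patients needs two sets of patients with no overlap. The protocol names this test, but its design provides only one set. Section 6.2 assigns the analysis to a third-party consultant, who would have to either omit a prespecified test or choose a comparator that the protocol does not name. A comparator chosen once the data are in hand would not be prespecified, and its p-value could be taken for a planned safety result.

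This is the only formal safety test in the plan. Without it, the document does not say how the adverse event proportion will be estimated, with what precision, or over which subjects.

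**Working it through.** The issue is structural, so the check is to take each possible pair of groups and compare it with the text.

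1. **Two concurrent arms.** None exist. All subjects are to receive the same lens combination (Sections 4.1 and 5.3), the total of 40 is not split (Section 6.1), and group assignment is not applicable (Section 9.3).
2. **Symphony eyes against Synergy eyes.** The Fisher sentence counts patients, and each patient is to have one lens of each kind, so patients cannot be divided by lens. If the unit were changed to eyes, the two sets would be paired within patient, whereas Fisher's test assumes independent groups.
3. **Toric against non-toric.** Section 5.3 makes this choice depend on the amount of astigmatism. No section calls these treatment groups or plans to compare them.
4. **Historical bilateral Synergy cohort.** Section 6.2 names it for visual symptoms, satisfaction and spectacle independence. Adverse events are not on that list. Visual symptoms are collected by questionnaire, and Table 1 lists questionnaires and adverse events on separate rows. The cohort's size and the source of any adverse event data are not given.

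No candidate fits the sentence as written. With all 40 patients in one row and an empty second row, the odds ratio is undefined and p = 1 whatever the event count. That follows by construction and does not measure the size of the problem.

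**What 40 subjects can support.** The plan gives no adverse event rate and no precision target, so there is no figure of its own to reproduce. Section 6.1 justifies 40 by a rule of thumb of at least 30 subjects for estimating a parameter. The matching summary is a one-group proportion x/n with an exact (Clopper-Pearson) 95% interval:

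- lower limit = the 0.025 quantile of Beta(x, n − x + 1), taken as 0 when x = 0
- upper limit = the 0.975 quantile of Beta(x + 1, n − x)

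For x = 0 and n = 40, the upper limit reduces to 1 − 0.025^(1/40) = 0.0881.

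Here n = 40 comes from Section 6.1, and the event counts are assumed because the documents give none:

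| Patients with an event (assumed) | Proportion | Exact 95% interval |
|---|---|---|
| 0/40 | 0% | 0 to 8.8% |
| 1/40 | 2.5% | 0.1 to 13.2% |
| 2/40 | 5.0% | 0.6 to 16.9% |
| 4/40 | 10.0% | 2.8 to 23.7% |

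Even with no events, a true rate of up to about 9% would remain compatible with the data. Reporting the interval makes that limit visible.

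**Denominator.** Section 4.3 removes subjects with aborted surgery from efficacy only and keeps their adverse events in reporting. Section 5.5.2 replaces subjects who leave between the two surgeries, so the number of subjects in whom surgery was started can exceed 40. Section 6.3 does not say which number it will use.

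**The case against.** The strongest counter-argument is that this is leftover template wording with little consequence. The study calls itself a pilot, safety is not among the endpoints in Section 2, and an analyst who found no second group would simply omit the test. This stands as a limit on importance. It does not make the sentence executable, and the general allowance in Section 6.2 for other suitable tests does not supply a comparison group for a test that is specifically named.

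A second objection concerns the tabulation sentence. It names no unit and could mean tabulation by lens, which would be sensible. This also stands. The patient-as-unit argument applies only to the Fisher sentence, and the tabulation sentence needs clearer wording only.

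A reader might infer from the silence on the denominator that subjects with aborted surgery will be dropped from safety reporting. The documents do not support that. Section 4.3 confines their exclusion to efficacy, says they are monitored for safety, and requires their adverse events to be reported. The denominator is a point to clarify.

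A reader might also infer that an underpowered adverse event comparison with the historical cohort is planned. Section 6.2 does not say so. Any power figure would rest on an assumed cohort size and assumed event rates for a comparison that no section describes, so none is given here.

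**Conclusion.** The Fisher comparison in Section 6.3 is wrong as written: it requires a second group of patients, and the documents provide none for adverse events. This conclusion rests on the text alone and needs no numerical assumption. The intervals above do depend on assumed event counts, and they show only what a cohort of 40 can support.

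The consequence is limited. The binocular defocus curve, which is the primary endpoint, is untouched, and adverse events can still be described. The point is worth correcting because it affects the plan's only formal safety test and the correction costs almost nothing.

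**What to change.** In Section 6.3:

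- Delete the Fisher sentence. In its place, report the proportion of patients with adverse events with an exact (Clopper-Pearson) 95% confidence interval.
- Replace the reference to each group with tabulation of ocular adverse events by eye and lens.
- As a clarification, define the safety denominator as all subjects in whom study surgery was started, consistent with Section 4.3. Note that it can differ from 40.
- Note that follow-up within the study is shorter for subjects who exit early. Table 1 schedules adverse event collection at surgery and Visit 3, while Section 4.3 returns subjects with aborted surgery to standard clinic follow-up.
- If the sponsor did intend the historical bilateral Synergy cohort as comparator, name it in Section 6.3 and give its size and the source of its adverse event data.

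The cost is rewording one paragraph, with no additional patients or visits. The downside is that there will be no between-group safety p-value.

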7. DATA HANDLING AND RECORD KEEPING

7.1. Confidentiality

To ensure confidentiality in this study, records of the participants will be examined only by the principal investigator and research staff involved in the study. Study records will be kept on file. Any statistical analysis and publication will not include any subject identifiers. Medical records will be made available only for review by the investigators, Sponsor Company or Research Institution, the IRB, and other State or Federal Regulatory Agencies, if necessary. All information in these records will be kept confidential.

7.2. Records Retention

The PI is accountable for the integrity, retention and security of all study related data. The investigator must maintain accurate, complete and current records relating to the clinical study. The investigator must maintain the required records during the investigation and for a period of 2 years after the date on which the investigation is terminated or completed then records will be scanned and kept electronically in a secured server.

8. STUDY MONITORING, AUDITING, AND INSPECTING

The nature and location of all source documents will be identified to ensure that original data required to complete the case report forms (CRFs) exist and are accessible for verification. If electronic source records are maintained, these records must be 21 CFR Part 11 compliant and will be printed and certified for verification as needed.

Required examination must be recorded on the CRFs. CRFs will be used as source document. All data reported must have corresponding entries in the source documents. The principal investigator or sub-investigator must review the reported data and certify that the CRFs are accurate and complete. No subject identifiers should be recorded on the CRFs beyond subject number, subject initials and study specific identifiers.

Data from CRFs will be entered into a database. Upon completion of the CRFs, the data will be reviewed by study designated personnel and statistician for accuracy and completeness. If corrections and/or any additions to the data are deemed necessary, queries will be generated. Designated research staff expected to respond to data queries in a timely manner and ensure that the corrections and changes made to the data in the database are reflected in the subjects' source documentation. Any changes will need to be initialed and dated by the authorized personnel making such changes.

Data will not be sold to third parties.

9. INVESTIGATIONAL PRODUCT

9.1. Description

The Symphony IntelliLight IOL (DXR00V or DXW150 – 375 – Toric II IOL) combines an echelette design (to create an extended depth of focus) with an achromatic technology (to correct chromatic aberrations) and a violet-light filter that diminishes the perception of visual disturbances such as halo, glare and starburst. The lens has been designed to provide high quality vision up to 26 inches so patients may still need to wear glasses for some activities mainly at near.

The Synergy IOL (DR00V or DFW150-375 – Synergy Toric II IOL) using TECNIS Simplicity Delivery System is a presbyopia correcting IOL designed to improve intermediate and

near vision, while maintaining distance visual acuity. This continuous range of focus lens provides a full range of vision and increased spectacle independence.

9.2. Treatment/Dosing Regimen

The IOL will be implanted at time of uncomplicated routine cataract surgery. Intraocular lenses are implantable medical devices and are intended for long term use over the lifetime of the patient.

9.3. Method for Assigning Subjects to Treatment/Dosing Groups

N/A

9.4. Subject Compliance Monitoring

Since the IOL is implanted at time of cataract surgery, subject compliance will not be an issue in this particular study.

9.5. Packaging, Receiving, Storage, Dispensing and Return

N/A

10. ETHICAL CONSIDERATIONS

This clinical trial will be conducted in accordance with the principles of the Declaration of Helsinki, and Good clinical practice. The Investigator and all clinical trial staff will conduct the clinical trial in compliance with this protocol. The Investigator will ensure that all personnel involved in the conduct of the clinical trial are qualified to perform their assigned duties through relevant education, training, and experience. Deviations from the clinical protocol must be documented in each subject's study records including the dates and reasons for each deviation. The PI must ensure that all aspects of the trial follow the applicable regulatory laws and conditions of approval imposed by the IRB.

11. IN CASE OF AN INJURY RELATED TO THIS RESEARCH STUDY

Every effort to prevent study-related injury will be taken by the study doctor and staff. In the event a patient is injured as a direct result of the study while following the study instructions and requirements, the patient will be instructed to immediately contact the principal investigator and/or study staff. Treatment will be provided as needed for those injuries caused directly by this research study. In the event of injury or illness caused by or occurring during the participation in this study, all charges for medical care provided will be billed to the patient's insurance company. The medical care costs for injuries or illnesses that are not caused directly by the research study will not be covered.

